### **Analysis Plan and Power Calculations:**

We will test the hypothesis that RMs/UMs (1 or 2 gain-of-function alleles) in the genotype-supported arm have better GERD and symptom control than RMs/UMs in the conventional treatment group because they will have their dose increased based on their genotype.

Continuous variables will be compared between the genotype-supported group and the conventional treatment group using the Student's unpaired *t*-test, and categorical variables will be compared using the chi-square or Fisher's exact test. The hypotheses will be tested using linear regression analysis to estimate the difference in the RDQ reduction in the RM/UM patients between the two arms. All analysis will be performed in SAS 9.4 (Cary, NC).

We will evaluate the percentage of the time when a dosing recommendation was made and accepted by the treating clinician, to provide practical data on the willingness of clinicians to adopt this approach. We will also collect patient- and provider-level survey data on knowledge, attitudes, and beliefs about pharmacogenetics testing, using survey tools adapted from other IRB-approved studies.

Power calculation. While there are no data in the literature on genotype associations with the efficacy endpoint we will use (symptom improvement), there are pH probe data by genotype that were generated by the Nemours investigators, that we can use, and this should be an excellent surrogate for symptom data. We have done power calculations based on two of the pH-based response phenotypes, found in Table 3. Specifically we powered based on percent time with pH < 4 (which has an effect size of 0.79) and acid clearance time (effect size of

0.45). Based on these two phenotypes, we have the following power to detect differences in efficacy between *CYP2C19\*17* carriers and non-carriers:

Based on the previous data for acid clearance time, with 180 total participants (120 from UF Health and 60 from Nemours), we have 81% power to detect a 0.49 effect size.

Based on the previous data for time with pH <4.0, with 180 participants, we have >99% power to detect a 0.79 effect size.

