Genetic results and clinical decision support. Results will be entered in the participant's electronic health record; genotype results for participants in the control/conventional arm will not be made available to patients/families through the secure patient portal in the EMR to maintain blind status. PPI recommended dosing will be made available to GI providers in the EMR for genotype-guided dosing. PPI templates will include phenotype, genotype, dosing recommendations, and educational information. Participants in the conventional arm will be prescribed the conventional PPI dose.

To minimize risks associated with genetic studies, all results of genetic tests and patient data will be stored in a secure database which is accessible only to study investigators. Genotype and phenotype data will be stripped of all identifiers prior to submission to the NIH dbGAP repository.

Assessment of PPI adverse events and efficacy. Our primary outcome will be a directed interview and questionnaire by study personnel at baseline and every following week up to 12 weeks of participation for efficacy of PPI therapy and for adverse outcomes for the study period: upper respiratory infection (cold), sore throat, strep throat, bronchitis, pneumonia, ear infection, acute sinusitis (sinus infection), and gastroenteritis. We have experience using the questionnaire to evaluate the safety of PPI treatment in children. The prevalence of each respiratory and gastrointestinal symptom will be compared in participants receiving conventional vs. genotype-supported dosing. As secondary outcomes, the efficacy and safety (adverse event score) of PPI therapy will be determined from scores from patient and parent-proxy reported outcomes: the GASP-Q, the validated SN-5 Pediatric Sinonasal Symptom Survey and validated PedsQL™ Gastrointestinal Symptoms Module. Efficacy and adverse events questionnaires will be completed via an electronic questionnaire on a weekly basis and stored in REDCap.

At Nemours Children's Hospital continuous monitoring on study metrics will be offered by study staff. Study metrics will include Gasp-Q, PedsQL™ Gastrointestinal Symptoms Module, SN-5 Pediatric Sinonasal Symptom Survey and Safety Q.

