- Gastrointestinal problems under scope includes; stomach pain and hurt; stomach upset; food and drinks limits; trouble swallowing; heartburn and reflux; gas and bloating; constipation; diarrhea; worry; medicines and communication will be measured.
- On the other hand; sinus infection; nasal obstruction; allergy symptoms; emotional distress; activity limitations and overall quality of life are some of the metrics to be evaluated for sinus and/or nasal problems.
- Each metric has its own scoring scale. Gastrointestinal problems will range from 0-100 for "Never" to "Almost always", respectively. Sinus and/or nasal problems have a 1-7 scale for "None of the time" to "All of the time", respectively.
- Safety Assessment (adverse event score) of PPI therapy will be scores from a questionnaire comprised of 7 respiratory symptoms: upper respiratory infection (cold); sore throat; strep throat; bronchitis; pneumonia; ear infection; acute sinusitis (i.e. sinus infection)

Monitoring for adverse events will be performed by the treating medical staff, the Principal Investigators, the site investigators, and the research coordinator(s). We will follow the guidance from the Office for Human Research Protections (OHRP) DHHS: Guidance on Reviewing and Reporting unanticipated Problems Involving Risks to Subjects or Others and Adverse Events <http://www.hhs.gov/ohrp/policy/AdvEvntGuid.htm>. Any event that: (1) involves harm, or an increased potential for harm, to one or more participant(s), or others, AND (2) is unexpected, AND (3) is related, or probably related, to study procedures will be reported to the Nemours and or UF IRB within 5 days of discovery, or within 24 hours if an unforeseen death. We will follow FDA guidelines for report of adverse events to the FDA within the required timeframe for the event. Additional standard institutional IRB reporting guidelines for adverse event reporting will also be followed.

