Statistical analysis. We will have two primary hypotheses tested in this pragmatic clinical trial: 1. Hypothesis: RMs (1 or 2 GOF alleles) in the genotype-supported arm have better GERD control than RMs in the usual care group 2. Hypothesis: PMs (1 or 2 LOF alleles) in the genotype-supported group have fewer adverse effects (composite of URI/GI infections, kidney adverse effects, bone fracture) than PMs in the usual care group. Continuous variables will be compared between the genotype-supported group and the usual care group using t-test, and categorical variables will be compared using the chi-squared test. The hypotheses will be tested by logistic regression analysis to estimate the odds ratios and 95% confidence intervals for GERD control rate in the RM patients between the two arms and for the adverse events between the PM patients between the two arms. Time to-event analysis will be performed using Kaplan Meier method and a Cox regression model. Significant covariates associated with the events will be adjusted for in the multivariable models. All analysis will be performed in SAS 9.4 (Cary, NC).

We will also have a composite analysis that is conducted in the same manner that combines efficacy and safety and tests the hypothesis that genotype supported PPI dosing leads to better PPI efficacy and safety, as determined by composite of refractory GERD, and adverse effects.

Finally, we will evaluate the influence of genotype-supported dosing recommendations and will evaluate the percentage of the time when a dosing recommendation was made and accepted by the treating clinician, to provide practical data on the willingness of clinicians to adopt this approach. We will also collect patient- and provider-level survey data on attitudes about pharmacogenetics testing; using survey tools adapted from those utilized by other IGNITE groups. These will be shared for network-wide analyses, but because of the number of patients we will study, we should also have sufficient data to perform analyses on our patients along.

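### Nemours tests efficacy in rapid metabolisers by logistic regression on an undefined GERD control rate, although it collects symptom scores weekly and UF tests the same contrast on a score

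*Combined protocol and SAP*

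**What the plan says.** **Nemours protocol, Statistical analysis.** The first of two primary hypotheses is that "RMs (1 or 2 GOF alleles) in the genotype-supported arm have better GERD control than RMs in the usual care group". The test is stated as follows: "The hypotheses will be tested by logistic regression analysis to estimate the odds ratios and 95% confidence intervals for GERD control rate". The paragraph gives no instrument, threshold or time point for control. It also plans a t-test for continuous variables between the two arms as a whole, Kaplan-Meier and Cox analyses, and adjustment for covariates found to be significant.

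**Nemours protocol, Assessment of PPI adverse events and efficacy.** The primary outcome is described as an interview and questionnaire at baseline and each week up to 12 weeks. The scores come second: "As secondary outcomes, the efficacy and safety (adverse event score) of PPI therapy will be determined from scores". The instruments named are the GASP-Q, the SN-5 and the PedsQL Gastrointestinal Symptoms Module. Collection is frequent: "Efficacy and adverse events questionnaires will be completed via an electronic questionnaire on a weekly basis and stored in REDCap". The metrics list that follows includes a heartburn and reflux domain and gives the scale: "Gastrointestinal problems will range from 0-100 for" the range from never to almost always.

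**UF protocol, section 7, Analysis Plan and Power Calculations.** The hypothesis is that RMs/UMs in the genotype-supported arm "have better GERD and symptom control than RMs/UMs in the conventional treatment group". It is tested by "linear regression analysis to estimate the difference in the RDQ reduction in the RM/UM patients between the two arms". The power statement takes 180 patients, 60 of them from Nemours, and expects about 30 RM/UM patients per arm. It claims 80% power for an effect size of at least 0.74 in the RDQ score.

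**The concern.** The two sites ask the same question about the same genotype group. UF answers it with a difference in mean score change and Nemours with an odds ratio for an event that is not defined. Three things are at stake.

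- **Information.** If control means falling on one side of a threshold on a symptom score, the test discards how far each patient is from that threshold. The Nemours RM group is too small to give that away.
- **Freedom of choice.** With no instrument, cut-off or week fixed, the outcome can be settled after data are seen, in an open-label trial whose staff are not blinded.
- **The shared sample size.** UF's power claim is for the RDQ and relies on the Nemours children. Nemours lists other instruments and makes a proportion its hypothesis test.

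**Working it through.** **Inputs**
- RM/UM share: 28% + 5.3% = 33.3% (Table 1).
- RMs per arm: Nemours 60 × 0.333 / 2 ≈ 10; UF 120 × 0.333 / 2 ≈ 20; both sites 180 × 0.333 / 2 ≈ 30. Dropout is ignored.
- Effect: d = 0.74, UF's figure for the RDQ. Applying it to a paediatric score is an assumption, because the documents give no SD for the Nemours scores.
- Alpha 0.05, taken as two-sided.

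**1. The plan's own figures**
- UF: two-sample t-test with noncentrality d√(n/2). For n = 30, 0.74 × √15 = 2.87 on 58 df gives power of 80.5%. The stated 80% reproduces.
- Nemours: 600 × 0.33 / 2 = 99 RMs per arm and a relative risk of 1.35 for 80% power. This cannot be checked, because the usual-care control rate is not given. The two-proportion formula returns 80% only if that rate is about 54% (54% against 73%). At 50% it gives 71%, and at 60% it gives 91%. The same protocol's Study Design paragraph now has 180 patients, 60 of them children, so this statement has to be redone anyway.

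**2. Information kept when a normal score is cut**

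Relative efficiency = φ(z_p)² / [p(1 − p)], where p is the control rate.

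| p | Efficiency | Lost |
|---|---|---|
| 0.50 | 0.3989² / 0.25 = 0.637 | 36% |
| 0.60 | 0.3863² / 0.24 = 0.622 | 38% |
| 0.70 | 0.3477² / 0.21 = 0.576 | 42% |
| 0.80 | 0.2800² / 0.16 = 0.490 | 51% |

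The 36% at a median cut is the minimum.

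**3. Power at the Nemours size (10 RMs per arm)**
- On the score: noncentrality 0.74 × √5 = 1.65 on 18 df gives power of 34.7%. Reaching 80% would need d of about 1.32.
- On the binary outcome: with usual-care control rate p₁, the genotype arm has p₂ = Φ(z_p₁ + 0.74). Power is that of the uncorrected chi-square test, by enumerating all outcomes.

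| p₁ | p₂ | Power |
|---|---|---|
| 36% | 64% | 23% |
| 50% | 77% | 21% |
| 60% | 84% | 18% |
| 70% | 90% | 14% |

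The only related figure in the documents is treatment failure in up to 40% of patients, which points to control of 60% or more. The usual normal approximation is slightly higher (23% at p₁ = 50%, 21% at 60%).

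**4. UF without the Nemours children**

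For n = 20 per arm, 0.74 × √10 = 2.34 on 38 df gives power of 63%. Power of 80% needs d of about 0.91 instead of 0.74.

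**The case against.** The strongest reply is that control need not be a cut of a score. The primary outcome is an interview and questionnaire, and the composite analysis uses refractory GERD, which is a responder idea. Control could therefore be a clinical classification. A responder rate is also easy to interpret and matches the relative risk in the Nemours power statement. This stands in part. The documents do not show that a score is being dichotomised, so the loss figures are conditional. But the same silence leaves the primary outcome undefined, and weekly scores still play no part in the stated RM test.

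A reader might infer four stronger things that the documents do not support:

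- **That the scores are thrown away.** They are kept as secondary outcomes and a t-test is planned. What is missing is a score-based test in RMs; about two-thirds of each arm are not RM/UM.
- **That baseline is ignored.** Baseline is not named, but significant covariates are to be adjusted for, and control could be defined relative to baseline.
- **That the sites cannot be combined.** The UF Resource Sharing Plans allow de-identified data to be shared for cross-site analysis. The plan simply gives no method. The obstacle to the RDQ claim is the instrument, and a linear model at Nemours would not remove it. Different instruments in children under a separate protocol are not in themselves an error.
- **That the better analysis rescues the Nemours test.** About 35% power is inadequate as well. The contrast at 30 per arm (80% on the score, 54-61% binary at control rates of 60-40%) matches no planned analysis, because no logistic regression of the pooled RM group is proposed.

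**Conclusion.** The point holds in this form: the Nemours RM efficacy test rests on an undefined binary outcome, the continuous scores already being collected are not used for it, and UF tests the same contrast on a different instrument and effect scale while counting Nemours patients in its RDQ power.

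The size is conditional. If control is a cut of one roughly normal score, at least 36% of the information is lost, and 36-51% for control rates of 50-80%. With d = 0.74 borrowed from UF and about 10 RMs per arm, power falls from about 35% to 14-23% over usual-care control rates of 36-70%. The missing definition and the RDQ mismatch depend on neither assumption. This is an analysis choice that should be improved. It does not by itself invalidate the trial.

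**What to change.** - **Nemours Statistical analysis.** Make the RM/UM efficacy test a linear regression of one prespecified, GERD-relevant continuous score at the final week on arm, with the baseline score as covariate. Candidates are the GASP-Q or the heartburn and reflux items of the gastrointestinal module. The whole module also covers constipation, diarrhoea, worry and communication, which could dilute a reflux effect. Name the analysis week, since the protocol speaks of 8-12 weeks, and confirm that the chosen score is completed at baseline.
- **Control rate.** State its instrument, cut-off and week, and report it with its odds ratio as a supportive summary.
- **Combining sites.** If this is wanted, use a standardised difference stratified by site.
- **Power statements.** Do not count Nemours patients in UF's RDQ calculation, and restate the Nemours calculation for the current sample size.

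The cost is analysis-plan wording; no new data are needed. The odds ratio becomes secondary, and a standardised effect is harder to interpret clinically than a control rate. The change makes better use of the data but leaves the Nemours test underpowered alone, and the plan should say so.

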## 7. Research Plan:

The study is a randomized, open-label, comparative effectiveness clinical trial in 180 total patients with GERD or dyspepsia symptoms who will be randomized to either conventional or genotype-supported treatment of GERD and dyspepsia. A total of 120 patients will be enrolled in the UF Health Gastroenterology Clinics in Gainesville, and 60 will be enrolled in a parallel study (under separate IRB protocol) at Nemours Children's Hospital Gastroenterology Clinics in Orlando, FL. Each site will be responsible for overseeing patient care and research at their respective facility. All participants will have symptoms of GERD or related diseases and be candidates for PPI therapy or on PPI therapy with continued symptoms.

We will enroll a total of 180 patients between the UF Health and Nemours sites, which should allow for sufficient power to detect our efficacy endpoint (see power calculation below). We will also collect data from the health records for up to 24 months after enrollment on upper respiratory infection (cold), sore throat, strep throat, bronchitis, pneumonia, ear infection, acute sinusitis (sinus infection), bone fractures, renal function, and gastrointestinal infections for preliminary assessment of the effects of *CYP2C19*-supported PPI dosing on adverse effects. This exploratory arm will provide data to inform power calculations for a larger study focused on preventing PPI-associated adverse events through genotype-supported dosing.

**Inclusion Criteria.** A total of 120 patients with GERD or related symptoms will be enrolled at UF Health. An additional 60 patients will be enrolled at Nemours Children's Hospital Gastroenterology Clinics under a separate IRB protocol. For this protocol, any patient over the age of 17 who presents to GI clinic with GERD or related symptoms and is either 1) being initiated on PPI therapy or 2) continues to have symptoms despite PPI therapy will be considered eligible for the study.

Exclusion Criteria. This study will exclude patients who have had extensive esophageal or gastric surgery or any major chronic illness or condition that in the opinion of the gastroenterologist that would interfere with participation in the study.

Participant Recruitment Methods.

Prior to enrolling their patients, clinicians at participating GI clinics (investigators for this study) will be asked to complete surveys that assess their knowledge, attitudes, and beliefs as they relate to pharmacogenetics testing.

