Assessment of PPI efficacy and adverse effects. Our primary outcome will be the effectiveness of PPI therapy, which will be determined via two questionnaires: RDQ and GOS scale, administered by study personnel at baseline and 12 weeks. The RDQ was developed to monitor treatment response over time and evaluates 6 symptoms (12 items) covering 3 domains: heartburn, regurgitation, and upper abdominal pain. Each symptom is evaluated using a 6-point Likert scale to assess frequency and severity over the previous week. Each symptom is rated from 1 (did not have) to 6 (severe), and the RDQ mean score is calculated as the mean response to the 12 items. The RDQ mean score thus ranges from 1 to 6 and has been psychometrically validated. The GOS scale evaluates 18 symptoms, with each rated from 1 (no problem) to 7 (very severe). Similar to the RDQ, the mean score is calculated as the mean response to the 18 items, with mean scores ranging from 1 to 7. Patient participation will end after they complete the approximate 12 week questionnaire. However, we will continue to

follow patients over 24 months through medical record review to assess adverse outcomes for occurrence of upper respiratory infection (cold), sore throat, strep throat, bronchitis, pneumonia, ear infection, acute sinusitis (sinus infection), bone fractures, renal function and gastrointestinal infections.

Metrics for assessing success of pharmacogenetic testing in clinical practice. We will test a variety of variables that will provide insight into attitudes and acceptability of pharmacogenetic testing. These will include: 1) percent of patients approached about the study who agree to participate; 2) surveys of patients and clinic staff on knowledge, attitudes, and beliefs about pharmacogenetic testing; and 3) the percent of the time a dosing recommendation for a patient in the genotype-supported arm is accepted by the clinician. Patients will be surveyed about knowledge, attitudes, and beliefs about pharmacogenetic testing using questionnaires on enrollment and at the end of their study participation. Clinic staff will be surveyed about knowledge, attitudes, and beliefs about testing at the beginning and end of the study.

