With 180 total patients (90 patients in each arm), we expect approximately 30 patients in each arm to have the genotype of interest (i.e. RM or UM). At alpha of 0.05, we will have 80% power to detect effect size of  $\geq 0.74$  in the RDQ score in RMs/UMs. This effect size is equivalent to a RDQ score difference of 1.22 for regurgitation and a score difference of 0.93 for heart burn. These differences in RDQ scores are smaller than what is considered clinically significant. Therefore our study is well-powered.

In summary, by studying a total 180 patients (120 from UF Health and 60 from Nemours), the data suggest we will have excellent power to detect an efficacy endpoint. Data generated from this protocol on adverse effects will also help us define the incidence of the adverse effect phenotypes to inform sample size for a future pragmatic trial examining effects of genotype-supported dosing on PPI safety endpoints.

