Study Design. The study is a randomized, open-label, comparative effectiveness clinical trial in 180 patients (60 children, 120 adults) with GERD or any stomach acid mediated condition that will require a PPI. Patients will volunteer to be randomized to either conventional PPI treatment or genotype-supported PPI treatment. All participants will have symptoms of GERD or related diseases who are candidates for PPI therapy or who are on PPI therapy and classified as refractory GERD. Adult patients will be enrolled at UF Health Gastroenterology Clinics and children will be enrolled at the Nemours Children's Hospital Gastroenterology Clinics. After obtaining informed consent, participants will be genotyped and randomly assigned to either conventional treatment or genotype-supported PPI therapy using a randomization table. At NCH, study participants in the control/conventional arm will be blinded on CYP2C19 metabolizer status. Study staff members will not be blinded to any study procedures or determinations as this will improve and facilitate study feasibility. At the end of study period (i.e. 8-12 weeks) study participants in the control/conventional arm will be revealed of metabolizer phenotype status. We will also collect data from the health records for up to 24 months after enrollment on upper respiratory infection (cold), sore throat, strep throat, bronchitis, pneumonia, ear infection, acute sinusitis (sinus infection), bone fractures, renal function, and gastrointestinal infections for preliminary assessment of the effects of CYP2C19-supported PPI dosing on adverse effects.

Participation stipends. Each participant will receive \$25 dollars at the end of study participation. Participants must have completed all study procedures by the end of the study period in order to receive the complete study stipend. If a study participant decides to withdraw from study before the end of study period (before 3 months), the participant will receive a pro-rated stipend. A deposit will be provided in a single CT Payer master card. Each participant will be provided a CT Payer (master card) at the moment of consent. The CT Payer card will be uploaded with the stipend at the end of study participation. Participants whom insurance coverage is limited, a separate deposit will be provided to cover study therapy expenses. We expect to incur in study drug expenses for participants with higher PPI dose prescriptions than conventional dosing (i.e. RMs and UMs).

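### UF adults and Nemours children are counted as one sample, but no arm comparison prespecifies site as a stratum

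*Combined protocol and SAP*

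**What the plan says.** **One sample.** The Nemours Study Design paragraph describes a "comparative effectiveness clinical trial in 180 patients (60 children, 120 adults"). The UF power calculation counts the same total: "With 180 total patients (90 patients in each arm), we expect approximately 30 patients in each arm to have the genotype of interest". The Nemours power calculation also counts both sites together, at 600 participants. The UF Resource Sharing section foresees cross-site analysis without saying how the sites would be combined.

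**Two protocols.** UF section 7 says of the children that "60 will be enrolled in a parallel study (under separate IRB protocol"). The sites differ as follows.

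| | UF | Nemours |
|---|---|---|
| Age | over 17 | 5 to 17 |
| Efficacy instruments | RDQ and GOS, baseline and week 12 | GASP-Q and PedsQL Gastrointestinal Symptoms Module (with the SN-5), weekly; RDQ and GOS not listed |
| Event ascertainment | record review: "follow patients over 24 months through medical record review to assess adverse outcomes" | "Efficacy and adverse events questionnaires will be completed via an electronic questionnaire on a weekly basis", plus record review for up to 24 months |
| Genotype-based advice | dose increase for RM and UM; usual doses otherwise, with a note on PMs | dose change for PM, IM, RM and UM |

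**Allocation and analysis.** Both texts randomise patients individually from a randomization table and name no stratification factor. UF plans t-tests, chi-square or Fisher tests, and a linear regression of RDQ reduction in RM/UM patients, with no covariate rule. Nemours plans t-tests, chi-square tests, Kaplan-Meier, Cox and a logistic model for "odds ratios and 95% confidence intervals for GERD control rate in the RM patients between the two arms". It then says that significant covariates will be adjusted for in the multivariable models.

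**The concern.** Age group, protocol, questionnaires and method of finding events all change together with site. Site may therefore predict the outcome strongly, and a comparison that ignores it treats the between-site spread as random error. The tested groups are small genotype subgroups. Even if each site keeps its own allocation list, the arms need not be balanced by site within RM/UM or PM/IM patients.

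The covariate sentence in the Nemours part answers this only in part. It makes the inclusion of site depend on the data, and it does not reach the t-test, chi-square or Kaplan-Meier comparisons. A pooled figure shown alone would also hide whether two differing interventions and ascertainment methods gave similar results.

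**Working it through.** **1. The plan's own figure.** The UF power calculation states: "At alpha of 0.05, we will have 80% power to detect effect size of" 0.74 or more, with about 30 RM/UM patients per arm. A two-sided two-sample t-test (noncentral t, n = 30 per arm, d = 0.74) gives 80.5%, so the figure reproduces. Sidedness is not stated; two-sided is assumed.

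**2. Cost of omitting site, linear model.** Let p be the share of children and D the site difference in within-site SDs. Pooling inflates the variance by 1 + p(1 − p)D². Here p = 60/180 = 1/3, so p(1 − p) = 2/9, and the effective d is 0.74/√(1 + 2D²/9). D is an assumption.

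| D (SD) | Variance ratio | Power without site | Loss from 80.5% (points) |
|---|---|---|---|
| 0.25 | 1.014 | 79.9% | 0.5 |
| 0.5 | 1.056 | 78.3% | 2 |
| 0.75 | 1.125 | 75.7% | 5 |
| 1.0 | 1.222 | 72.2% | 8 |
| 1.5 | 1.500 | 63.4% | 17 |

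This table supposes a continuous outcome measured at both sites. On the text as it stands, the RDQ is not one.

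**3. Cost of omitting site, GERD control as yes/no.** The Nemours power calculation gives no baseline control rate. A relative risk of 1.35 with 99 RMs per arm and 80% power implies about 54%. With an overall baseline of 0.536, OR 2.27, 30 RMs per arm, one-third children and 20,000 simulated trials per setting:

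| Assumed site gap in control rate | Without site | With site | Loss (points) |
|---|---|---|---|
| 10 points | 30.9% | 31.6% | 0.7 |
| 20 points | 29.2% | 30.7% | 1.5 |
| 30 points | 27.6% | 29.6% | 2 |
| 40 points | 24.4% | 27.6% | 3 |

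Simulated type I error was 4.7% to 5.2% with or without the site term. At the 600-patient size still used in the Nemours power calculation (99 RMs per arm, 42% children), the loss is 0.6 to 7 points over the same gaps.

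**4. A more extreme case, adverse events.** Assume a control risk of 70% in children, 10%, 20% or 30% in adults, and a within-site OR of 0.42. Mantel-Haenszel power is compared with an unstratified score test.

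| Patients | Adults 30% | Adults 20% | Adults 10% |
|---|---|---|---|
| All 180 | 72 vs 66% | 64 vs 53% | 51 vs 37% |
| 60 (RM/UM size) | 30 vs 27% | 25 vs 21% | 20 vs 15% |

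Table 1 gives 20% + 1.7% IM/PM, so 180 × 0.217 = 39 patients. In that subgroup, stratifying changes power by about 2 points or less in either direction.

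**5. Chance mix.** The SD of the between-arm difference in child share is √[p(1 − p)(2/n)]. At n = 30 this is √[(2/9)(2/30)] = 0.122, a 95% range of ±1.96 × 0.122 = ±24 points. A 20-point site gap then moves a risk difference by up to 0.24 × 20 ≈ ±5 points. A 0.5 SD site difference moves a mean difference by up to ±0.12 SD.

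**6. Who can contribute to the RDQ comparison.** RM plus UM is 28% + 5.3% = 33.3% in Table 1. Among 120 adults that is about 40, or 20 per arm. Power at d = 0.74 is then 62.6%, and 80% power needs d of about 0.91.

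**The case against.** The strongest reply is that the Nemours covariate rule already deals with the cases that matter. In the all-180 settings of step 4, site is significant in at least 99.9% of simulated trials, and power under the rule equals stratified power. With 60 patients it comes within 1 point of it. Where the gap is too small to trigger the rule, little is lost: at 50% versus 30% risk with 180 patients, about 1 point. This stands as an answer on power in the Nemours logistic model. It does not cover the unadjusted comparisons or the UF analysis plan, and it leaves a design variable to a significance test.

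Several stronger readings are tempting, and the documents do not support them:

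- **Losses of 6 to 14 points.** These arise only in an all-180 analysis with an assumed 40- to 60-point event gap that no section gives. The named hypotheses concern RMs and PMs. At most, the all-patient figures fit the additional efficacy-and-safety composite.
- **A biased odds ratio.** In step 4 the pooled odds ratio moves from 0.42 to between 0.48 and 0.56. In large part this is non-collapsibility: the marginal odds ratio is a different quantity, not a wrong one.
- **A false positive from age mix.** Chance imbalance widens the spread of the estimate, and the test already reflects that.
- **Weekly forms at one site, records only at the other.** Record review is planned at both sites; the weekly forms are an addition at Nemours.

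**Conclusion.** The omission is real and its numerical cost is modest. Children and adults are pooled in the sample-size reasoning, and no arm comparison prespecifies site. In the tested genotype subgroups the loss is about 0 to 5 power points for site gaps up to 0.75 SD or, for yes/no outcomes, 60 percentage points. It reaches 8 points in the linear model at 1.0 SD and is essentially nil if the sites do not differ. Chance mix adds noise, with child share differing by up to about 24 points at 30 per arm, while type I error stays near 5%.

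These figures assume two-sided tests, 1:1 allocation, no dropout, a common within-site effect and between-site gaps that the documents do not supply. The case for change rests mainly on interpretation and on the change being nearly free.

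A reader might infer that a site term would make a pooled RDQ analysis sound. It would not, because the Nemours text lists no RDQ data to pool. GERD control likewise has no stated definition common to the two sites' scales.

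**What to change.** In the UF Analysis Plan and the Nemours Statistical analysis paragraph, state that:

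1. Every analysis combining UF and Nemours is stratified by site regardless of significance: Mantel-Haenszel for proportions, a forced site term in the linear and logistic models, and a stratum in Cox and Kaplan-Meier. Unadjusted t-tests and chi-square tests on combined data are replaced by these.
2. Site-specific estimates with confidence intervals appear beside each pooled estimate.
3. Pooling is limited to outcomes measured at both sites, with one stated definition of GERD control if that outcome is pooled.
4. The RDQ comparison is reported for adults only, with power restated on about 20 RM/UM patients per arm, unless the children's study also collects the RDQ.

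Items 1 and 2 cost wording and one model parameter, since site is known for every patient. In very small subgroups, stratifying can itself cost up to about 2 power points when the gap is modest. Items 3 and 4 need a definition agreed between the sites and a revised power statement, but no new data unless the RDQ is added at Nemours.
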